15. APPENDICES

Appendix 1. Schedule of assessments

Assessments			Tre	eatment I	Period					End of Studyi
Study Day(s)	Day 1ª	W4* ± 5 days	W8* ± 5 days	W12 ± 5 days	W24 ± 10 days	W36 ± 10 days	W48 ± 10 days	Q12 Wks ± 10 days	Q24 Wks ± 10 days	
Informed Consent/Assent	X							unjs	unjs	
Eligibility Assessment	X									
Medical History	X									
Physical Examination b	X	X	X	X	X		X		X	X
Vital Signs ^c	X	X	X	X	X		X			X
Adverse Events	X	X	X	X	X		X		X	X
Concomitant Medications	X	X	X	X	X		X		X	X
Hematology/Chemistry analyzed by Central Laboratory (US and Europe only) ^d	X	X	X	X	X		X			X
Hematology/Chemistry analyzed by Local Laboratory (ex-US and ex-Europe only) ^{d, e}	Xª	X	X	X	X		X		X f	Х
Exploratory Laboratory CCI (US and Europe Only)	X			X	X		X			
Urine Pregnancy Test ^g	X	X	X	X	X		X		X	X
Drug Dispensing and Accountability ^h	X			X	X	X	X	X	X	Х

Assessments		Treatment Period							End of Studyi	
Study Day(s)	Day	W4*	W8*	W12	W24	W36	W48	Q12	Q24	
	1ª	± 5	± 5	± 5	± 10	± 10	± 10	Wks	Wks	
		days	days	days	days	days	days	± 10	± 10	
								days	days	

Amendment 3

Abbreviations: Q = every; W = week; Wks = weeks

- * Participants from GBT440-031 who received GBT440 900 mg or placebo, or who received voxelotor for less than 12 weeks will have additional assessments at Week 4 and Week 8.
- a. Eligibility assessments will be determined on Day 1 prior to dosing. If labs were done for GBT440-031 or this study within 7 days of Day 1, they do not need to be repeated on Day 1.
- Abbreviated Physical Exam which includes: general appearance, examination of eyes, skin, cardiovascular and respiratory systems, an abdominal examination and a symptom directed examination.
- c. Vital signs (heart rate [HR], blood pressure [BP]) will be collected after a participant has rested for at least 5 minutes in the seated or supine position. A repeated measurement of HR and BP will be taken if the first reading is outside the normal range and deemed clinically significant.
- d. Hematology assessments will include: red blood cell (RBC), hematocrit (Hct), hemoglobin (Hb), platelets, white blood cell (WBC), we reticulocytes, absolute reticulocytes, RBC distribution width (RDW), mean corpuscular volume (MCV) and mean corpuscular hemoglobin concentration (MCHC). After Week 48, hematology assessments should only be performed per standard of care.

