# 2.1. Study Design

Study GBT440-034 is a multicenter, global, open-label extension (OLE) study available to participants who were previously enrolled and treated in Study GBT440-031. Participants must meet the entry criteria for this study to be eligible for enrollment.

All participants enrolled in GBT440-034, regardless of treatment received in the parent study GBT440-031 (i.e., placebo, voxelotor 900 mg, or voxelotor 1500 mg), receive treatment with voxelotor 1500 mg once daily (the highest dose deemed safe for continued assessment based on GBT440-031).

All participants in Study GBT440-034 have scheduled study visits with assessments at Day 1, Week 12, Week 24, and Week 48, and then every 24 weeks thereafter. Participants who were treated with placebo or voxelotor 900 mg in Study GBT440-031 have additional study visits with assessments at Week 4 and Week 8.

Participants may receive voxelotor in GBT440-034 as long as they continue to receive clinical benefit which outweighs risk as determined by the Investigator and/or until the participant has access to voxelotor from an alternative source (i.e., commercialization or through a managed access program).

Additional details and background information are provided in the study protocol.

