# **4.2.** Safety Population

The safety population includes all enrolled participants who received treatment with study drug (voxelotor) during Study GBT440-034.

The safety population will be the primary analysis population for this study.

Analyses will be presented for overall population, and by prior treatment group (i.e., placebo, voxelotor 900 mg, and voxelotor 1500 mg) based on treatment received in the parent study GBT440-031, as appropriate.

<sup>a Including Week 72, End of Treatment, or End of Study laboratory values collected in Study GBT440-031.

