#### **5.3.3.** Clinical Laboratory Assessments

Laboratory abnormalities assessed by the Investigator as clinically significant will be recorded as adverse events.

For participants enrolled in the US and Europe, laboratory values were collected at regular timepoints per the Schedule of Assessments up to Week 48 and analyzed by a central laboratory. After Week 48, laboratory assessments were collected per standard of care for clinical management.

For participants enrolled outside of the US and Europe, laboratory values were collected at regular timepoints per the Schedule of Assessments up to Week 48 and analyzed by each individual site's local laboratory. After Week 48, laboratory assessments were collected per standard of care for clinical management, except for hemoglobin and clinical measures of hemolysis (% reticulocytes, absolute reticulocytes, and bilirubin [total, direct, and indirect]), which continued to be collected every 24 weeks per the Schedule of Assessments.

Descriptive summaries of laboratory parameters (e.g., hematology and serum chemistry) for all participants at baseline and each evaluation post baseline through Week 48, as well as changes from baseline over time, will be provided. If any of the results are below the limit of quantitation or above the limit of quantitation, then the numerical limit will be used in the descriptive summaries.

In addition, laboratory values for hemoglobin and clinical measures of hemolysis collected via local laboratories for participants outside of the US and Europe for all scheduled timepoints (including beyond Week 48) will be summarized descriptively.

Central laboratory values will be graded for selected parameters using the NCI CTCAE. Laboratory abnormality shifts from baseline grade to maximum grade post-baseline up to Week 48 will be tabulated. All assessments after study drug initiation until 28 days after discontinuation of study drug will be included in identifying the maximum grade post-baseline.

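### If shown by prior treatment group, the laboratory shift table takes the worst grade over five scheduled draws in the prior-placebo and prior-900 mg groups but three in most of the prior-1500 mg group

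*SAP*

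**What the plan says.** SAP 5.3.3 defines the table: "Laboratory abnormality shifts from baseline grade to maximum grade post-baseline up to Week 48 will be tabulated". On which samples count, it adds: "All assessments after study drug initiation until 28 days after discontinuation of study drug will be included in identifying the maximum grade post-baseline". On the source of the grades: "Central laboratory values will be graded for selected parameters using the NCI CTCAE". Protocol 7.1.5 and Appendix 1 restrict central-laboratory analysis to US and Europe participants, so the table covers them only.

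SAP 2.1 gives all participants "scheduled study visits with assessments at Day 1, Week 12, Week 24, and Week 48, and then every 24 weeks thereafter". In addition, those "treated with placebo or voxelotor 900 mg in Study GBT440-031 have additional study visits with assessments at Week 4 and Week 8". The central-laboratory row of Appendix 1 is marked at Weeks 4, 8, 12, 24 and 48 and is blank at Week 36. Protocol 7.1 and Appendix 1 also give Weeks 4 and 8 to anyone with less than 12 weeks of prior treatment, an exception that SAP 2.1 does not repeat.

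SAP 4.2 presents analyses overall and "by prior treatment group (i.e., placebo, voxelotor 900 mg, and voxelotor 1500 mg) based on treatment received" in the parent study, where appropriate. Neither document limits the maximum grade to visits that all groups share, or adjusts for the number of samples.

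**The concern.** A participant's worst grade cannot fall as samples are added. The number of scheduled samples is set by prior treatment, which is also the variable that would define the columns. A side-by-side table would therefore compare a worst-of-five with a worst-of-three.

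The two extra draws fall in the first eight weeks after voxelotor is started (prior placebo) or raised (prior 900 mg), when a true early laboratory effect might appear. Higher percentages in those columns could come from the drug, from the extra draws, or from both, and this table could not say which. The analyses are descriptive, so no error rate is at stake. What is at stake is the reading of the percentages, since readers will compare them directly.

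**Working it through.** The documents give no abnormality rate for this table, so there is no planned figure to reproduce. The check counts the draws and then asks what equal risk would produce.

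**Step 1: scheduled post-baseline central-laboratory draws up to Week 48** (SAP 2.1; Protocol 7.1 and Appendix 1)
- Prior placebo and prior 900 mg: Weeks 4, 8, 12, 24, 48, so k = 5.
- Prior 1500 mg: Weeks 12, 24, 48, so k = 3. Those with under 12 weeks of prior treatment have k = 5; their number is not given.

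**Step 2: equal risk, independent samples.** Let p be the chance that one sample grades worse than baseline (assumed, 1% to 20%). Then P(any worsening) = 1 − (1 − p)^k. At p = 5%: 1 − 0.95^5 = 22.6% and 1 − 0.95^3 = 14.3%, ratio 1.59.

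**Step 3: correlated samples.** Use a probit model with a participant-level random intercept U (standard normal) and latent correlation ρ (assumed): P = 1 − E[(1 − Φ((z_p + √ρ·U)/√(1 − ρ)))^k], where z_p is the standard normal quantile at p.

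| p | ρ = 0: 5 vs 3 draws (ratio) | ρ = 0.5 | ρ = 0.9 |
|---|---|---|---|
| 1% | 4.9% vs 3.0% (1.65) | 4.0% vs 2.6% (1.51) | 2.2% vs 1.8% (1.25) |
| 5% | 22.6% vs 14.3% (1.59) | 16.6% vs 11.8% (1.40) | 9.4% vs 8.0% (1.19) |
| 10% | 41.0% vs 27.1% (1.51) | 29.2% vs 21.8% (1.34) | 17.4% vs 15.0% (1.16) |
| 20% | 67.2% vs 48.8% (1.38) | 48.8% vs 38.9% (1.25) | 31.3% vs 27.8% (1.12) |

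A beta-binomial model, in which the correlation of 0.5 applies to the yes/no outcomes themselves, gives 11.0% vs 8.9% (1.23) at p = 5% and 21.0% vs 17.4% (1.21) at p = 10%. Both lie inside the same range.

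**Step 4: sensitivity at p = 5%, ρ = 0**
- If 10% of the prior-1500 mg group had under 12 weeks of treatment (assumption), their column becomes 0.9 × 14.26% + 0.1 × 22.62% = 15.1%, and the ratio falls from 1.59 to 1.50.
- With one further sample in every group (6 vs 4), such as an early end-of-study draw: 26.5% vs 18.5%, ratio 1.43.

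**Step 5: common visits only.** With k = 3 in every group, equal risk gives equal expected percentages (14.3% each at p = 5%, ρ = 0), ratio 1.00.

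**The case against.** - **The split is not certain.** SAP 4.2 applies the by-group display only where appropriate, SAP 5.3.3 does not say that this table is split, and SAP 6 leaves layouts to a separate document. This stands: with an overall table alone, no between-group contrast arises.
- **Other displays inform the contrast.** A reader might infer that this table is the study's only view of starting or raising voxelotor against continuing it. The documents do not support that. SAP 5.3.3 also plans summaries of values and changes at each evaluation through Week 48, using the separate windows of SAP Table 1. Clinically significant abnormalities are also reported as adverse events. These displays do not give each person's worst grade, however, so they do not correct this table.
- **The groups are not simply new starters and continuers.** A reader might call both five-draw groups new starters. That fits prior placebo only; prior-900 mg participants already took voxelotor in the parent study.
- **The size is assumed, and may be small in absolute terms.** At p = 1% with independent samples the gap is under 2 points; in the beta-binomial case at p = 5% it is about 2 points. With 60 participants per group (assumption), the standard error of that last difference is about 5.5 points. This tempers the importance of the point. It does not remove a bias whose direction is set by the schedule.
- **Worst grade over all samples is a sound safety choice.** It avoids missing values in the early weeks. This stands, and it is why the planned maximum should be kept and not replaced. A footnote giving draws per group would disclose the imbalance without correcting it.

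**Conclusion.** The point holds conditionally. If the shift table is shown by prior treatment group, its columns rest on five scheduled draws against three, apart from prior-1500 mg participants with under 12 weeks of treatment. At equal per-sample risk, apparent worsening in the prior-placebo and prior-900 mg columns is then expected to be inflated by a ratio of roughly 1.1 to 1.65. That range rests on assumed p from 1% to 20% and latent correlation from 0 to 0.9, and inflation vanishes if abnormalities fully persist within a person. Unscheduled and end-of-study samples also enter the maximum and can shift the counts in any group.

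The point concerns the interpretation of one descriptive table for US and Europe participants. A reader might conclude that the table will certainly show a spurious excess, or that an early effect could not be seen anywhere in the report. The documents support neither conclusion; the limit applies within this table.

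**What to change.** In SAP 5.3.3:
- Keep the all-assessment maximum as planned, overall and by group, so that no safety value is hidden.
- Add a by-prior-treatment panel giving the maximum grade over the Week 12, 24 and 48 analysis windows of SAP Table 1 only.
- Show the Week 4/8 maximum separately, for participants who have those visits.
- State the number of samples per participant by group.

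The cost is one extra panel in a descriptive table, with no new data. The added panel omits Week 4/8 values, which stay visible alongside it.

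The change equalises scheduled sampling and nothing else. Under SAP 3.1 the baseline is the last value on or before first dose in this study, including late parent-study values. It may therefore be on drug for prior-1500 mg participants and off drug for prior-placebo participants. A footnote should say so, and the columns should not be described as fully comparable.

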#### 5.3.4. Electrocardiogram Assessments

ECGs (12-lead) were initially performed for GBT440-034 study participants who received placebo or voxelotor 900 mg in the parent study GBT440-031. However, based on results from Study GBT440-0115 (a dedicated thorough QT study in healthy participants in which no effects on QT were observed), ECG collection was no longer required in GBT440-034 as of 20 August 2019. The limited ECG data collected in this study will be provided in a listing.

#### 5.3.5. Vital Signs

Descriptive summaries of vital signs (e.g., systolic blood pressure, diastolic blood pressure, and heart rate) at baseline and each evaluation post baseline to Week 48, as well as changes from baseline over time, will be generated.

## **5.4. SCD-Related Complications**

## 5.4.1. Frequency of SCD-Related Complications

SCD-related complications include adverse events of acute chest syndrome, hepatic sequestration, leg ulcers, osteonecrosis, pneumonia, priapism, pulmonary hypertension, retinopathy, scleral icterus, sickle cell anaemia with crisis, splenic sequestration, and stroke.

The incidence and the annualized incidence rate of each SCD-related complication based on TEAEs, as well as the total of all SCD-related complications, will be computed. Annualized incidence rates will be estimated by dividing the total number of complications observed for all participants by the total assessment time for all participants, and 95% confidence intervals provided based on exact Poisson confidence limits.

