7.1.7. Other SCD-related Complications

SCD-related complications will be collected and assessed over the duration of the study.

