7.2.2.5. Worsening of Sickle Cell Disease

Complications and symptoms of SCD should be recorded as an AE or SAE if judged by the Investigator to have worsened in severity and/or frequency or changed in nature during the study.

7.2.3. Serious Adverse Events, Serious Adverse Drug Reactions, and Requirements for Immediate Reporting

All SAEs, regardless of causal attribution, occurring on this study will be recorted on the AE eCRF and reported to Pfizer Safety via PSSA within 24 hours of the Investigator, designee, or site personnel's knowledge of the event. In the event that the EDC system is not available, paper SAE report forms will be used to report the SAE and faxed or emailed to Pfizer Safety.

The information reported on the paper SAE report form should be entered into PSSA once available.

The Sponsor may request additional information pertaining to the SAE from the investigational site. Follow-up reports must be submitted within 24 hours of awareness as additional information becomes available.

All SAEs regardless of causal attribution must be followed to resolution, stabilization or until reasonable attempts to determine resolution of the SAE are performed.

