8.1.1.2. Frequency of SCD-Related Complications

Over the course of the treatment period, the frequency of SCD complications for each participant will be recorded. SCD complications may include the following: VOC, acute chest syndrome, hepatic sequestration, leg ulcers, priapism, pulmonary hypertension, retinopathy, scleral icterus, splenic sequestration, and stroke. The incidence and rate of each complication and the totality of all SCD-related complications will be computed and then compared to those observed in the GBT440-031 study.

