#### 2. INTRODUCTION

The objective of Study GBT440-034 (C5341022) is to assess the long-term safety and treatment effect of voxelotor in participants with sickle cell disease (SCD) who have completed treatment in Study GBT440-031.

This statistical analysis plan (SAP) provides details of the planned analyses and statistical methods for Study GBT440-034 final clinical study report (CSR). Where this document differs from the high-level analysis plan described in the study protocol, the methodology described in this SAP is considered the latest and supersedes the corresponding section(s) in the protocol.

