## 2.2.2. Sickle Cell Disease (SCD)-Related Complications

Frequency of SCD-related complications of long-term dosing with voxelotor. SCD-related complications include adverse events with preferred terms of acute chest syndrome, hepatic sequestration, leg ulcers, osteonecrosis, pneumonia, priapism, pulmonary hypertension, retinopathy, scleral icterus, sickle cell anaemia with crisis, splenic sequestration, and stroke.

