#### **5.3.2.** Adverse Events

Adverse events will be classified according to MedDRA; the most current version at the time of analysis will be used. Severity of adverse events will be graded using the National Cancer Institute Common Terminology Criteria for Adverse Events (NCI CTCAE) version 4.03, when possible, or based on the protocol-specified grading for adverse events not covered in the NCI CTCAE.

Non-SCD-related adverse events and SCD-related adverse events will be summarized separately. SCD-related adverse events include sickle cell anaemia with crisis, acute chest syndrome, pneumonia, priapism, and osteonecrosis. All other adverse events will be considered non-SCD-related.

Summaries of TEAEs, defined as adverse events with an onset on or after the date of informed consent until 28 days after last dose of study drug, will be tabulated by MedDRA system organ class (SOC) and preferred term, as appropriate.

Summaries of TEAEs will be provided for the following categories:

- Non-SCD-related TEAEs
- Non-SCD-related TEAEs by study year
- Non-SCD-related TEAEs by maximum severity
- Non-SCD-related TEAEs assessed as related to study drug by the investigator
- Non-SCD-related TEAEs of rash (group term)
- Non-SCD-related TEAE of abdominal pain (group term)
- Non-SCD-related treatment-emergent serious adverse events (SAEs)
- Non-SCD-related treatment-emergent SAEs by study year
- Non-SCD-related treatment-emergent SAEs assessed as related to study drug by the investigator
- SCD-related TEAEs
- SCD-related TEAEs by study year
- SCD-related TEAEs by maximum severity
- SCD-related TEAEs assessed as related to study drug by the investigator

- SCD-related treatment-emergent SAEs
- SCD-related treatment-emergent SAEs by study year
- SCD-related treatment-emergent SAEs assessed as related to study drug by the investigator
- All TEAEs leading to study drug discontinuation
- All TEAEs leading to study drug dose modification (dose reduction or interruption)

Listings for all adverse events, adverse events leading to study drug discontinuation, SAEs, and deaths will be provided.

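### SAP 5.3.2 labels as non-SCD-related seven adverse event terms that SAP 2.2.2 and 5.4.1 count as SCD-related complications

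*SAP*

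**What the plan says.** SAP section 5.3.2 summarises SCD-related and non-SCD-related adverse events separately and draws the line as follows: "SCD-related adverse events include sickle cell anaemia with crisis, acute chest syndrome, pneumonia, priapism, and osteonecrosis. All other adverse events will be considered non-SCD-related".

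SAP section 2.2.2 defines the complications endpoint through adverse event terms: "SCD-related complications include adverse events with preferred terms of acute chest syndrome, hepatic sequestration, leg ulcers, osteonecrosis, pneumonia", and the list goes on. Section 5.4.1 repeats that list. After acute chest syndrome it continues with "hepatic sequestration, leg ulcers, osteonecrosis, pneumonia, priapism, pulmonary hypertension, retinopathy, scleral icterus, sickle cell anaemia with crisis, splenic sequestration, and stroke". The numerator of its rates is also taken from adverse event records: "The incidence and the annualized incidence rate of each SCD-related complication based on TEAEs".

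Protocol section 8.1.1.2 gives the list that the endpoint started from: "SCD complications may include the following: VOC, acute chest syndrome, hepatic sequestration, leg ulcers, priapism, pulmonary hypertension, retinopathy, scleral icterus, splenic sequestration, and stroke".

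On precedence, SAP section 2 says that where the two documents differ, "the methodology described in this SAP is considered the latest and supersedes the corresponding section(s) in the protocol".

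**The concern.** Both analyses draw on the same records, namely treatment-emergent adverse events. A stroke recorded as a TEAE enters the 5.4.1 rates as an SCD-related complication. Under 5.3.2 the same record goes into the non-SCD-related tables and is absent from the SCD-related ones. If it is serious, the same happens in the SAE tables.

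Long-term safety and the frequency of SCD complications are both stated objectives of the study. A reader of the report would find two different divisions of the same events and no explanation. Someone who looks only at the non-SCD-related SAE table could take a splenic sequestration for an event unconnected with the disease. Someone who looks only at the SCD-related SAE table would not see it at all.

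**Working it through.** No sample size or test is involved, so the check compares lists and counts tables.

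**Inputs**
- SAP 5.3.2, SCD-related terms (5): sickle cell crisis, acute chest syndrome, pneumonia, priapism, osteonecrosis. A closing sentence puts every other event in the other group.
- SAP 2.2.2 and 5.4.1, SCD-related complications (12): those five, plus stroke, splenic sequestration, hepatic sequestration, retinopathy, pulmonary hypertension, leg ulcers and scleral icterus. The two sections give the same twelve.
- Protocol 8.1.1.2, SCD complications (10): VOC, acute chest syndrome, priapism, and the same further seven.

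**Step 1: the difference within the SAP.** The five terms are a strict subset of the twelve, and 12 − 5 = 7 terms are left over. As a share of list entries this is 7/12 = 58%.

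**Step 2: comparison with the protocol.** All seven are in the protocol's list of ten, so 7/10 = 70% of the named complications are non-SCD-related in 5.3.2. The other three match the five-term list, if VOC is equated with sickle cell anaemia with crisis. The remaining two of the five, pneumonia and osteonecrosis, are not named in protocol 8.1.1.2. The count of seven does not depend on how VOC is matched.

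**Step 3: how many 5.3.2 summaries depend on the list.**

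| Group | Summaries | Can change with the list |
|---|---|---|
| Non-SCD-related | 9 (TEAEs; by year; by severity; drug-related; rash; abdominal pain; SAEs; SAEs by year; drug-related SAEs) | 7 |
| SCD-related | 7 (the same, without rash and abdominal pain) | 7 |
| All TEAEs | 2 (discontinuation; dose modification) | 0 |
| Total | 18 | 14 |

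The rash and abdominal pain groups are left out on the assumption that none of the seven terms falls in them: 9 − 2 = 7, and 7 + 7 = 14.

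**Step 4: can another clause settle it?** The precedence statement in SAP section 2 ranks the SAP above the protocol. It does not rank one SAP section above another.

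**The case against.** The best defence is that the two lists serve different purposes. One divides the adverse event tables and the other defines a complications endpoint, and the labels differ (adverse events in one, complications in the other). The choice may be deliberate. The table mock-ups are in a separate document (SAP section 6) and may carry a footnote that cannot be seen here. But sections 2.2.2 and 5.4.1 define complications as adverse events, so the difference in label does not separate the records. Nor can the five-term list be read as mere examples, because the sentence that follows it closes it. If two lists are intended, the SAP should say so and give the reason.

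The defence is right about weight. Section 5.3.2 tabulates by system organ class and preferred term, all adverse events, SAEs and deaths are listed, and 5.4.1 counts all twelve terms. It would be wrong to infer that events disappear. The 58% and 70% are shares of list entries, not of events, and 14 of 18 is a ceiling.

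A reader might also infer that the 5.4.1 rates are under-counted. Protocol section 7.2.2.5 says that SCD complications and symptoms "should be recorded as an AE or SAE if judged by the Investigator to have worsened in severity and/or frequency or changed in nature", whereas section 7.1.7 says that "SCD-related complications will be collected and assessed over the duration of the study". The documents do not support that inference:
- Section 7.2.2.5 says if, not only if.
- Protocol 7.2 has all adverse events recorded. Section 7.2.1.1 treats new events as adverse events and inpatient hospitalisation as a criterion for an SAE.
- Protocol 7.1.7 and 8.1.1.2 call for collection with no condition of worsening, and the SAP's TEAE definition adds none.
- Nothing shows that a site withheld an event, and no capture fraction is given.

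Section 5.4.1 already names TEAEs as its source. The different time windows of 5.4.1 (TEAEs, to 28 days after last dose) and 5.4.2 (to last dose) are each stated and belong to two separate outputs.

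**Conclusion.** The inconsistency is certain from the text. Seven adverse event terms are SCD-related complications in SAP 2.2.2 and 5.4.1 and non-SCD-related in 5.3.2, with no reason given, and all seven are named as SCD complications in protocol 8.1.1.2.

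The point is minor. All analyses are descriptive, so only classification is affected. At most 14 of the 18 summaries in 5.3.2 could change, and each does so only if at least one of the seven events occurs and meets that table's filter, for example a drug-related SAE. The documents do not give the number of such events, so the number of tables that would really change cannot be derived. The ceiling of 14 rests on the assumption about the rash and abdominal pain groups. The conclusion does not extend to under-counting of complications, which is not shown.

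**What to change.** Change the SAP only, in one of two ways:

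1. Replace the five-term list in 5.3.2 with the twelve-term list of 2.2.2 and 5.4.1. The number of listed complications classed as non-SCD-related falls from seven to zero.
2. Keep the five-term tables, add one summary of TEAEs and SAEs divided by the twelve-term list, and footnote the 5.3.2 tables with the reason for the two lists.

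The cost is small and no new data are needed. The first option changes the division in up to 14 summaries. If interim summaries used the five-term list, the final tables would no longer line up with them, and a note should say so. The second option keeps that continuity at the price of one extra summary and a footnote.
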